1 PROTOCOL SUMMARY

1.1 SYNOPSIS

Title:	The BREATHE Study: Bronchiolitis Recovery and the Use of High Efficiency Particulate Air (HEPA) Filters
Study Description:	This is a multi-center, parallel, double-blind, randomized controlled clinical trial. Children <12 months of age hospitalized with bronchiolitis are randomized 1:1 to receive a 24-week home intervention with filtration units containing HEPA and carbon filters (in the child's sleep space and a common room) to improve indoor air quality (IAQ) or to a control group with filtration units without HEPA and carbon filters. The HEPA intervention units and control units will be used for 24 weeks after pre-intervention IAQ measurements. Children are followed for respiratory outcomes over the pre-intervention and intervention periods.
Objectives:	Primary Objective: To determine if use of a HEPA filtration unit home intervention reduces the respiratory symptom burden (symptom-free days; SFD) for 24 weeks compared to a use of a control unit. Secondary Objectives: 
1. To test the efficacy of a HEPA filtration home intervention, relative to the control arm, on difference in number of unscheduled healthcare visits for respiratory symptoms over 24 weeks.2. To test the efficacy of a HEPA filtration home intervention, relative to the control arm, on difference in quality of life (QOL).3. To test the efficacy of a HEPA filtration home intervention, relative to the control arm, on difference in particulate matter ≤ 2.5 micrometers in diameter ($PM_{2.5}$) levels in the home over 24 weeks.
Endpoints:	Primary Endpoint: Number of caregiver-reported SFDs over 24 weeks (SFD defined as a 24-hour period without coughing, wheezing, or trouble breathing). Secondary Endpoints: 
1. Caregiver-reported number of hospitalizations, Emergency Department (ED) or Urgent Care (UC) visits, or other unscheduled medical visits for respiratory complaints (cough, wheeze, or trouble breathing).2. Total QOL score, as measured by the PedsQL™ Pediatric Quality of Life Inventory Infants Scales questionnaire at the end of the intervention period.3. Weekly average $PM_{2.5}$ levels as measured by 2 in-home PurpleAir monitors over 24 weeks and scaled to the unit of micrograms per cubic meter ($\mu g/m^3$) per week.
Study Population:	Up to 228 children consented (enrolled), age <12 months (at admission), with their first hospitalization for bronchiolitis
Phase:	Not applicable

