1.3 SCHEDULE OF ACTIVITIES (SOA)

Table 2. Schedule of Activities (See MOP for definitions of "weeks.")

Evaluation/Procedures	Screen ¹ (hospital)	Enroll / Randomize In hospital (+1 week)	Pre-intervention Weeks 1-2 after hospital discharge ²	Intervention ² Weeks 3-26	Week 26 (End of Participation)
Review inclusion/exclusion criteria	x	x			
Informed consent		x			
Document participant characteristics and risk factors for recurrent wheeze ³		x			x
Pre-intervention period (in all study participant homes – both intervention and control): up to 2 weeks continuous home PM _{2.5} monitoring via PurpleAir ⁴			x		
Intervention period (in all study participant homes – both HEPA/control unit): Continuous home PM _{2.5} monitoring via PurpleAir ⁴				x	
Continuous HEPA/control unit use ⁵				x	
Continuous use of kilowatt meter to measure HEPA/control unit adherence ⁵				x	
Weekly submission: Symptom survey, number of medical visits, number of nights away from home, HEPA/control unit adherence ⁷			x	x	
Check-in contact with study team ⁶			x	x	
QOL Survey ⁷					x

¹ Screening and enrollment ideally will occur during hospitalization. However, enrollment can occur after discharge to home if the family can receive and set-up the air quality monitoring equipment ideally within 7 days of discharge. Other procedures can occur at home.

² Day of hospital discharge is defined as day 1. Intervention ideally starts on day 14.

³ See Table 4.

⁴ Families place PurpleAir monitors in the child's sleep space and in another common room. Baseline PM_{2.5} measurements are collected for up to 14 days and then the family will begin using HEPA units in the same rooms (child's sleep space and another common room) that contain the PurpleAir monitors while PM_{2.5} monitoring continues. HEPA units will have active filters in the intervention group and no HEPA or carbon filters in the control group.

⁵ Kilowatt-hour meter is used to measure actual HEPA unit use. All devices are simple to plug in. The study team will work with the family remotely to confirm correct installation and placement of the devices at baseline and at the start of HEPA use and confirm data transmission from the PurpleAir monitor.

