- **Healthcare visits:** The parent/guardian will record the number of hospitalizations, ED/UC visits, and other medical visits for respiratory symptoms. This will be a (Y/N) for whether they participant (child) had a healthcare visit in the past week. If Y, there will be a prompt to enter the number of visits for each visit type. If N, they will move on to the next section, "Time away from home."
- **Time Away from home:**
 - **Days away from home:** The parent/guardian will be prompted to enter how many days that week the child spent more than 6 hours outside the home (0-7 days).
 - **Nights away from home:** The parent/guardian will be prompted to enter how many nights that week the child spent away from their primary residence (away for vacation, staying with someone else, etc.) (0-7 days).
- **Equipment use:**
 - **HEPA/control unit use:** For each room with a HEPA/control unit, the parent/guardian will be asked to respond Yes/No to whether they used unit and asked to report the usual setting used (1, 2, 3, or 4). If applicable, the parent(s)/guardian(s) will also record the numerical reading visible on the kW meter attached to each HEPA/control unit. This will be a simple entry of the numbers displayed on the kW meter to respond to the survey prompt.
 - **PurpleAir monitor:** The parent/guardian will be asked whether the monitor is plugged in with the light on (Yes or No). They will also be asked whether the hot spot is on with bar light and 3 lighted dots on (Yes or No).

Quality of Life:

- The PedsQL™ Pediatric Quality of Life Inventory Infant Scales⁹⁸ questionnaire will be administered to a parent/guardian at the end of the intervention period. This is a validated outcome measure of QOL for infants 1-12 months (36 items) and 13-24 months (45 items). The constructs include 5 subdomains: physical functioning, physical symptoms, emotional functioning, and cognitive functioning.

The questionnaire will be administered online. The alternative will be for the research coordinator to obtain responses verbally.

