9 STATISTICAL CONSIDERATIONS

9.1 STATISTICAL HYPOTHESES

Primary Objective: To test the efficacy of a HEPA filtration unit home intervention, relative to the control arm, with respect to respiratory symptom burden (as measured by symptom-free days; SFD) over 24 weeks following activation of filtration.

Primary Endpoint: Number of caregiver-reported SFDs over 24 weeks following activation of filtration (SFD defined as a 24-hour period without coughing, wheezing, or trouble breathing)

Statistical Hypothesis: Mean of SFDs in the HEPA filtration home intervention group is larger than mean of SFDs in the control group.

Secondary Objective 1: To test the efficacy of a HEPA filtration home intervention, relative to the control arm, on the number of unscheduled healthcare visits for respiratory symptoms over 24 weeks following activation of filtration.

Secondary Endpoint 1: Caregiver reported counts of unscheduled healthcare visits from each of the metrics including hospitalizations, Emergency Department (ED) visits, Urgent Care (UC) visits, and other unscheduled medical visits for respiratory complaints (cough, wheeze, or trouble breathing). A sum of counts (or total counts) of all metrics is also used as the secondary endpoint.

Statistical Hypothesis 1: Mean of counts of unscheduled healthcare visits for respiratory symptoms in the intervention group is smaller than mean of counts of unscheduled healthcare visits for respiratory symptoms in the control group.

Secondary Objective 2: To test the efficacy of HEPA filtration home intervention, relative to the control arm, on difference in QOL.

Secondary Endpoint 2: Total QOL score, as measured by the PedsQL™ Pediatric Quality of Life Inventory Infants Scales questionnaire at the end of the intervention period.

Hypothesis 2: Child QOL will be higher in families that receive the HEPA intervention compared to controls.

Secondary Objective 3: To test the efficacy of HEPA filtration home intervention, relative to the control arm, on PM_{2.5} levels in the home over 24 weeks following activation of filtration.

Secondary Endpoint 3: Weekly average PM_{2.5} levels as measured by 2 in-home PurpleAir monitors over 24 weeks and scaled to the unit of $\mu\text{g}/\text{m}^3$ per week.

Hypothesis 3: Mean of PM_{2.5} level in the intervention group is lower than mean of PM_{2.5} level in the control group.

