## 5. Endpoints and Variables

**Table 1. Endpoints and variables**

Endpoint/Variable	Description
Primary Endpoint(s) 
 
➤ Number of caregiver-reported SFDs over 24 weeks
 
	
 
➤ The primary endpoint is the number of caregiver-reported symptom free days (SFD) over 24 weeks following activation of filtration (SFD is defined as a 24-hour period without coughing, wheezing, or trouble breathing).
 

Secondary Endpoint 1 
 
➤ Counts of unscheduled healthcare visits (UHV)
 
	
 
➤ Caregiver reported counts of unscheduled healthcare visits (UHV) from each of the metrics including 
 
• Hospitalizations
 
• Emergency Department (ED) visits or Urgent Care (UC) visits
 
• Other unscheduled medical visits for respiratory complaints (cough, wheeze, or trouble breathing)
 
• A sum of counts (or total counts) of all metrics
 
 
 

Secondary Endpoint 2 
 
➤ Total QOL score
 
	
 
➤ Total QOL score or Total Scale Score (TSS), is measured by the PedsQL™ Pediatric Quality of Life Inventory Infants Scales questionnaire at the end of the intervention period. Caregivers whose children are age 1-12 months will use a 36-item PedsQL; and those whose children are age 13-24 months will use a 45-item PedsQL. In each item, a score is assigned at 100 if the answer is “never a problem”; 75 if the answer is “almost never a problem”; 50 if the answer is “sometimes a problem”, 25 if the answer is “often a problem”; and 0 if the answer is “almost always a problem” respectively (Varni et al., 2011).
 

Secondary Endpoint 3 
 
➤ Weekly average PM2.5 levels
 
	
 
➤ Weekly average PM2.5 levels as measured by the average of the two in-home PurpleAir monitors over 24 weeks and scaled to the unit of <math>\mu\text{g}/\text{m}^3</math> per week.
 
➤ Weekly average PM2.5 levels as measured in each room separately of the two in-home PurpleAir monitors over 24 weeks and scaled to the unit of <math>\mu\text{g}/\text{m}^3</math> per week.
 

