#### **6.6.2. Analysis of Secondary Endpoints**

##### **Secondary Endpoint 1: UHVS**

For the secondary endpoint measure, we will test the following null hypothesis:

Null hypothesis: Mean of counts of unscheduled healthcare visits for respiratory symptoms in the intervention group will not differ from the mean of counts of unscheduled healthcare visits for respiratory symptoms in the control group.

vs

Alternative hypothesis: Mean of counts of unscheduled healthcare visits for respiratory symptoms in the intervention group is smaller than mean of counts of unscheduled healthcare visits for respiratory symptoms in the control group.

Caregiver reported counts of unscheduled healthcare visits (UHV) from each of the metrics including 1) hospitalizations; 2) Emergency Department (ED) or Urgent Care (UC) visits; 3) other unscheduled medical visits for respiratory complaints (cough, wheeze, or trouble breathing); and 4) A sum of counts (or total counts) of all metrics.

The counts of hospitalizations, ED or UC visits, and other unscheduled medical visits will be obtained from the caregiver's weekly survey or adverse event forms. The total count is the aggregation of counts of all unscheduled healthcare visits described above.

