### **SOURCE OF MISSING DATA**

Missing observations of primary endpoint of SFDs can occur if a caregiver fails to 1) complete and submit the weekly symptom survey in a week or in multiple weeks, or (2) complete all symptom questions in a weekly survey.

Missing observations of the secondary endpoint 1 of UHVs can occur if a caregiver fails to 1) complete and submit the weekly survey of healthcare visits in a week or in multiple weeks, or 2) report the counts of ED or UC visits and other medical visits for breathing problems.

Missing observations of the secondary endpoint 2 (total QOL score or TSS) can occur if a caregiver fails to complete and submit the PedsQL survey, or (2) complete all items in the PedsQL questionnaire.

Missing observations of the secondary endpoint 3 of PM2.5 can occur if (1) the PurpleAir monitor fails to function and read the air quality properly, (2) the child's family disables the PurpleAir monitor(s) intentionally or unintentionally, or (3) the participant does not return the PurpleAir monitor(s) and no WiFi hotspot data is available.

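### Secondary endpoint 1 is limited to unscheduled visits, but the survey as described is not, so planned respiratory visits may enter the other-visit count and the total

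*Protocol*

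**What the plan says.** **Endpoint.** Protocol 1.1 lists hospitalisations, ED or UC visits, "or other unscheduled medical visits for respiratory complaints (cough, wheeze, or trouble breathing"). Protocol Table 3 and 9.1, and SAP 3.5, Table 1 and 6.6.2, keep the same restriction. Protocol 9.1 adds a total: "A sum of counts (or total counts) of all metrics is also used as the secondary endpoint". SAP 6.6.2 builds it the same way: "The total count is the aggregation of counts of all unscheduled healthcare visits described above".

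**Data collection.** The healthcare-visit item in Protocol 8.1 reads: "The parent/guardian will record the number of hospitalizations, ED/UC visits, and other medical visits for respiratory symptoms". It opens with a yes/no question on whether the child had a healthcare visit in the past week, and continues: "If Y, there will be a prompt to enter the number of visits for each visit type". The schedule of activities in Protocol 1.3, repeated in SAP 3.3, has "Weekly submission: Symptom survey, number of medical visits, number of nights away from home, HEPA/control unit adherence". SAP 6.8, listing how this endpoint can be missing, refers to a caregiver failing to "report the counts of ED or UC visits and other medical visits for breathing problems".

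**Link between the two.** SAP 6.6.2 takes the hospitalisation, ED/UC and other unscheduled counts from the weekly survey or the adverse event forms. Neither document describes a planned-or-unplanned question, a derivation rule or adjudication.

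**The concern.** The hypothesis concerns unscheduled visits, while the item as described covers any medical visit for respiratory symptoms. Every participant has just been in hospital for bronchiolitis and receives usual care outside the study (Protocol 8.2). A booked recheck for cough or wheeze fits the described item literally, and a caregiver answering as asked could report it.

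Nothing described would remove such a visit later. The survey is described as collecting a count per visit type. Adverse event forms are unlikely to help with routine office visits, because Protocol 8.3.1 limits recording to severe events, serious events, and events associated with the intervention or study equipment.

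Two things are at stake. The trial could report a result on unscheduled visits from data that do not identify them. And if the filter leaves planned visits unchanged, adding them to both arms weakens the ratio that the log-link model in SAP 6.6.2 estimates.

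**Working it through.** **1. Is there a figure in the plan to reproduce?** Not for this endpoint. The only efficacy sizing is for symptom-free days: 98 per arm, a 20-day difference and SD 43, giving an effect size of 20/43 = 0.465 and 90% power. That reproduces (90.0% by the noncentral t) but has no bearing here. No visit rate, dispersion, rate ratio or planned share appears in either document.

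**2. Which counts are exposed?**
- Hospitalisations: only if a planned respiratory admission occurs.
- ED/UC visits: not touched by this wording gap.
- Other medical visits: exposed.
- Total: exposed, because it includes the other visits.

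**3. Which planned visits could be counted?** Only those after activation of filtration, where the 24-week window begins (Protocol 9.1). Activation is ideally on day 14 after discharge (Protocol 1.3), so rechecks in roughly the first two weeks fall outside.

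**4. Direction.** Let m be the control-arm mean of unscheduled visits, RR the true rate ratio, and p the mean number of planned visits per child, equal in both arms. The planned share of control-arm counted visits is f = p/(m + p).
- Observed ratio = (RR·m + p)/(m + p) = RR(1 − f) + f, which is nearer to 1 than RR.
- Observed difference in means = (RR·m + p) − (m + p) = (RR − 1)m, which does not contain p.

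**5. Illustration. All rates are assumptions.** Take 98 per arm, m = 2, RR = 0.70, negative binomial unscheduled visits with dispersion k = 0.5, and independent Poisson planned visits. The unscheduled variances are 2 + 0.5 × 2² = 4.00 (control) and 1.4 + 0.5 × 1.4² = 2.38 (HEPA). Planned visits add p to each.
- p = m·f/(1 − f)
- SE of the difference = √[(4.00 + 2.38 + 2p)/98]
- Power is for a two-sided 5% Wald test of the log ratio, by the delta method. It ignores the site effect.

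| Planned share f | p | Observed ratio | Difference | SE of difference | Power, log ratio |
|---|---|---|---|---|---|
| 0% | 0 | 0.70 | −0.60 | 0.255 | 66% |
| 10% | 0.22 | 0.73 | −0.60 | 0.264 | 63% |
| 20% | 0.50 | 0.76 | −0.60 | 0.274 | 60% |
| 30% | 0.86 | 0.79 | −0.60 | 0.287 | 56% |
| 50% | 2.00 | 0.85 | −0.60 | 0.325 | 46% |

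Example at f = 20%: 0.70 × 0.80 + 0.20 = 0.76, and √(7.38/98) = 0.274.

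**6. Range.** Over m from 1 to 3, k from 0.5 to 1.0 and RR from 0.6 to 0.7, power falls by about 3 to 9 points at f = 20% and about 11 to 27 points at f = 50%. A true ratio of 0.60 would appear as 0.68 at f = 20% and 0.80 at f = 50%.

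**The case against.** The strongest reply is that the actual survey form has not been seen. SAP 1 says the plan must be read with the data collection forms and survey tools, and Protocol 8.1 only summarises them. The summary is not complete: SAP 3.7 mentions a survey question about a red glow that Protocol 8.1 omits. The hypotheses in Protocol Table 3 and 4.1 also use *other medical visits* in parentheses to spell out unscheduled visits, so Protocol 8.1 may be using the same shorthand. And SAP 6.6.2 itself says the unscheduled count comes from the survey. This stands. A reader might infer from Protocol 8.1 that planned visits are in fact being counted as unscheduled; the documents show only that they may be.

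Frequency is also open. No passage says planned respiratory visits are common. The window omits the earliest rechecks, and Protocol 5.2 excludes several groups likely to have standing specialist follow-up, such as infants on home oxygen or with cystic fibrosis.

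Finally, SAP 6.6.2 reports the difference in average visits, and hospitalisations and ED/UC visits are already analysed separately. Both facts limit the damage. Neither supplies a rule for the other-visit count or the total.

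**Conclusion.** The mismatch is real and needs no assumption about rates: the endpoint is restricted to unscheduled visits, the described collection is not, and no separation rule is given. It affects the other-visit metric and the total.

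The effect on results is conditional. If planned visits are counted and are equal across arms, the ratio is pulled toward 1 and precision falls. It would be tempting to say that the treatment effect is diluted on every scale; that does not follow, because the difference in means is then unbiased and only its variance grows. If planned follow-up depends on symptoms or earlier visits, it may differ by arm, and the bias need not be toward no effect. The size cannot be stated from the documents; the tabulated figures only illustrate the mechanism.

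Nor do the documents support moving the unscheduled-visit test to a new composite of hospitalisations and ED/UC visits. Those metrics already have their own analyses, and the form may prove adequate.

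**What to change.** 1. Check the data collection form. If it already restricts the item to unscheduled visits, align the wording in Protocol 8.1 and SAP 6.8, and state the item's exact text in SAP 6.6.2. That closes the point.
2. If it does not, reword the item for remaining participants to *other unscheduled medical visits (not a planned check-up or follow-up) for cough, wheeze or trouble breathing*, and align Protocol 8.1 and SAP 6.6.2 and 6.8.
3. For data already collected with the broader item, label the other-visit count and the total as *medical visits for respiratory symptoms, planned or unplanned*.
4. In that case, prespecify hospitalisations plus ED/UC visits as a sensitivity analysis, before outcomes are seen by arm, and not as a replacement for the planned test.

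The cost is one survey phrase and some SAP text. The sensitivity count is sparser than the total, and counts taken before and after a rewording are not identical, so the report should say which participants answered which item.

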8.2 SAFETY AND OTHER ASSESSMENTS

This is a minimal risk study. No changes to standard of care therapies and standard medical treatment will be made for participants based on research data. Children will not receive medical care from the research team and will receive their usual care (such as from their primary care provider). Childproofing is necessary for all equipment to prevent injury to young children, and steps to determine family needs around childproofing will be outlined in the MOP. If circumstances arise such as a significant air pollution exposure that is expected to be prolonged (e.g., major wildfire with air quality impacts in the area) or other conditions where it is medically recommended by the child's health provider to use active HEPA filtration, the participant may be unmasked.

8.3 ADVERSE EVENTS AND SERIOUS ADVERSE EVENTS

8.3.1 DEFINITION OF ADVERSE EVENTS (AE)

An AE is any untoward or unfavorable medical occurrence in a human subject, including any abnormal sign, symptom, or disease, temporally associated with the volunteer's participation in research, whether or not it is considered related to the research intervention. Stable chronic conditions that are present prior to enrollment and do not worsen are not considered AEs and will be accounted for in the subject's medical history. Exacerbation or worsening of pre-existing conditions are defined as AEs. Each AE will be classified by the investigator as serious (SAE) or nonserious. All AEs will be evaluated for severity, action taken, seriousness, outcome, and relationship to the study intervention. Information on protocol-specific AEs, severe AEs, and SAEs will be collected from participant reports and via phone calls, as well as review of weekly surveys. Protocol-specific AEs, severe AEs and SAEs will be collected for the duration of the study. We will only record and track severe AEs; SAEs; and AEs associated with the study intervention and/or study equipment.

8.3.2 DEFINITION OF SERIOUS ADVERSE EVENTS (SAE)

An AE or suspected adverse reaction is considered "serious" if, in the view of either the investigator or sponsor, it results in any of the following outcomes:

- Death
- A life-threatening adverse event
- Inpatient hospitalization or prolongation of existing hospitalization
- Persistent or significant incapacity or substantial disruption of the ability to conduct normal life functions
- Important medical events that may not result in death, be life-threatening, or require hospitalization may be considered serious when, based upon appropriate medical judgment, they may jeopardize the participant and may require medical or surgical intervention to prevent one of the outcomes listed in this definition.

